9.4. Interim Analysis

An interim analysis may be conducted to support regulatory submissions if considered necessary by the sponsor.

9.5. Sample Size Determination

No formal sample size calculation has been planned for this phase 2 OLE study. Up to approximately 30 subjects who have completed the efgartigimod pSS studies will be enrolled for the OLE study.

10. SUPPORTING DOCUMENTATION AND OPERATIONAL CONSIDERATIONS

10.1. Appendix 1: Regulatory, Ethical, and Study Oversight Considerations

10.1.1. Regulatory and Ethical Considerations

- This study will be conducted according to the protocol and the following:
 - Consensus ethical principles derived from international guidelines including the Declaration of Helsinki and Council for International Organizations of Medical Sciences international ethical guidelines
 - Applicable ICH GCP guidelines
 - Applicable laws and regulations
- The protocol, protocol amendments, ICF, IB, and other relevant documents (eg, advertisements) must be submitted to an IRB/IEC by the investigator and reviewed and approved by the IRB/IEC before the study is initiated.
- Any amendments to the protocol will require IRB/IEC approval before implementing changes made to the study design, except for changes necessary to eliminate an immediate hazard to study participants.
- Protocols and any substantial amendments to the protocol will require health authority approval before initiation except for changes necessary to eliminate an immediate hazard to study participants.
- The investigator is responsible for providing the following:
 - Providing written summaries of the status of the study to the IRB/IEC annually or more frequently according to the requirements, policies, and procedures established by the IRB/IEC
 - Notifying the IRB/IEC of SAEs or other significant safety findings as required by IRB/IEC procedures
 - Providing oversight of the conduct of the study at the site and adherence to requirements of 21 CFR, ICH guidelines, the IRB/IEC, European regulation 536/2014 for clinical studies, and all other applicable local regulations

10.1.2. Financial Disclosure

Investigators and subinvestigators will provide the sponsor with sufficient, accurate financial information as requested to allow the sponsor to submit a complete and accurate financial certification or disclosure statements to the appropriate regulatory authorities. Investigators are responsible for providing information on financial interests during the study and for 1 year after completion of the study.

The following information will be collected: any significant payments from the sponsor such as a grant to fund ongoing research, compensation in the form of equipment, retainer for ongoing consultation or honoraria, proprietary interest in IMP, significant equity interest in the sponsor as defined in 21 CFR 54.2(b) (1998).

10.1.3. Informed Consent Process

- The investigator or representative will explain the nature of the study, including risks and benefits to the potential participant and answer all questions before the participant completes the informed consent process by signing the informed consent form
- Potential participants must be informed that their participation is voluntary. A statement of informed consent must be signed that meets the requirements of the IRB/IEC or study center, ICH guidelines, local regulations, and, where applicable, privacy and data protection requirements
- The medical record must include a statement that written informed consent was obtained before the participant was enrolled in the study and the date the written consent was obtained. The authorized person obtaining the informed consent must also sign the ICF
- Participants must be reconsented to the most current version of the ICF(s) during their participation in the study if the changes to the ICF impact participant participation
- A copy of the ICF(s) must be provided to the participant
- A copy of the ICF(s) must be provided to the participant
- Participants who are rescreened are required to sign a new ICF (Section 5.4)

10.1.4. Recruitment Strategy

Not applicable.

10.1.5. Data Protection

- The sponsor will assign participants a unique identifier. Any participant records or datasets transferred to the sponsor will contain the identifier only; participant names or any information that would make the participant identifiable will not be transferred
- The participant must be informed that the sponsor, sponsor representatives, competent authorities, etc., can review source data containing identifiers and will use their personal study-related data per local data protection law. The level of disclosure must also be explained to the participant who will be required to give consent for their data to be used as described in the informed consent
- The contract between sponsor and study sites specifies responsibilities of the parties related data protection, including handling of data security breaches and respective communication and cooperation of the parties
- Information technology systems used to collect, process, and store study-related data are secured by technical and organizational security measures designed to protect

such data against accidental or unlawful loss, alteration, or unauthorized disclosure or access

10.1.6. Committees Structure

Not applicable.

10.1.7. Dissemination of Clinical Trial Data

The sponsor will register and disclose the results of clinical studies as required by law.

10.1.8. Data Quality Assurance

- The sponsor or designee is responsible for the data management of this study, including quality checking of the data
- All participant data relating to the study will be recorded on eCRFs unless transmitted to the sponsor (or its designee) electronically (eg, laboratory data) or paper SAE forms. The investigator is responsible for verifying data entries are complete, accurate, and verifiable by electronically signing the eCRF
- Guidance on completing eCRFs is provided in the eCRF completion document
- The investigator must permit study-related monitoring, audits, IRB/IEC review, and regulatory agency inspections and direct access to source data documents
- Study processes, study sites (including but not limited to site visits, central laboratories, vendors), the study database, and study documentation can be subject to quality assurance audit during the study by the sponsor or sponsor's designee on behalf of the sponsor. In addition, inspections could be conducted by foreign or domestic regulatory bodies at their discretion. Such audits/inspections can occur during or after the completion of the study
- Records and documents, including signed ICFs, on the conduct of this study must be retained by the investigator for 25 years after study completion unless local regulations or institutional policies require a more extended retention period. Without the sponsor's written approval, no records will be destroyed during the retention period. No records are allowed to be transferred to another location or party without the sponsor's written notification
- Monitoring details describing strategy and activities are described in a monitoring plan:
 - Study monitors will perform ongoing source data verification to confirm that data entered into the eCRF by authorized site personnel are accurate, complete, and verifiable from source documents; that the safety and rights of participants are being protected; and that the study is being conducted following the currently approved protocol and any other study agreements, ICH GCP, and all applicable regulatory requirements

10.1.9. Source Documents

- Source documents provide evidence for the existence of the participant and substantiate the integrity of the data collected. Source documents are filed at the investigator's site
- Data entered in the eCRF that are transcribed from source documents must be consistent with the source documents or the discrepancies must be explained. The investigator may need to request previous medical records or transfer records, depending on the study. Also, current medical records must be available
- Definition of what constitutes source data, and its origin can be found in the monitoring plan
- The investigator must maintain accurate documentation (source data) that supports the information entered in the eCRF
- The sponsor or designee will perform monitoring to confirm that data entered into the eCRF by authorized site personnel are accurate, complete, and verifiable from source documents; that the safety and rights of participants are being protected; and that the study is being conducted in accordance with the currently approved protocol and any other study agreements, ICH GCP, and all applicable regulatory requirements

10.1.10. Study and Site Start and Closure

First Act of Recruitment

The study start date is the date on which the first participant rolls over to ARGX-113-2211.

Study/Site Termination

The sponsor or designee reserves the right to close the study site or terminate the study at any time for any reason at the sole discretion of the sponsor. Study sites will be closed upon study completion. A study site is considered closed when all required documents and study supplies have been collected and a study site closure visit has been performed.

The investigator could initiate study site closure at any time, provided there is reasonable cause and sufficient notice is given in advance of the intended termination.

Reasons for the early closure of a study site by the sponsor or investigator could include but are not limited to:

- For study termination:
 - Discontinuation of further compound development
- For site termination:
 - Failure of the investigator to comply with the protocol, the requirements of the IRB/IEC or local health authorities, the sponsor's procedures, or GCP guidelines
 - Inadequate or lack of recruitment (evaluated after a reasonable amount of time) of participants by the investigator

- Total number of participants included earlier than expected

If the study is prematurely terminated or suspended, the sponsor shall promptly inform the investigators, the IECs/IRBs, the regulatory authorities, and any contract research organization(s) used in the study of the reason for termination or suspension, as specified by the applicable regulatory requirements. The investigator will promptly inform the participant and ensure appropriate therapy and/or follow-up for the participant, as necessary.

10.1.11. Publication Policy

- The results of this study can be published or presented at scientific meetings. If this is foreseen, the investigator agrees to submit all manuscripts or abstracts to the sponsor before submission. This allows the sponsor to protect proprietary information and to provide comments
- The sponsor will comply with the requirements for publication of study results. In accordance with standard editorial and ethical practice, the sponsor will generally support publication of multicenter studies only in their entirety and not as individual site data. In this case, a coordinating investigator will be designated by mutual agreement
- Authorship will be determined by mutual agreement and consistent with International Committee of Medical Journal Editors authorship requirements

10.2. Appendix 2: Clinical Laboratory Tests

- The tests listed in [Table 6](#) will be performed as described in the Laboratory Manual
- Additional tests can be performed during the study as determined necessary by the investigator or required by local regulations
- Investigators must document their review of each laboratory test result

Table 6: Protocol-Required Laboratory Tests

Laboratory Test	Parameters		
Hematology	RBC count platelet count hemoglobin hematocrit	RBC indices: MCV MCH %reticulocytes	WBC count with differential: neutrophils eosinophils lymphocytes basophils monocytes
Serum chemistry	ALT AST GGT alkaline phosphatase albumin ^a	creatinine potassium BUN CRP glucose	sodium total protein ^a calcium bilirubin (total and direct)
Routine urinalysis	Specific gravity pH, glucose, protein, blood, ketones, bilirubin, urobilinogen, nitrite, leukocyte esterase Microscopic examination (if blood or protein is abnormal)		
Pregnancy testing	Urine test at baseline and other time points (as needed for WOCBP potential, defined in Section 10.4.1)		

ALT = alanine aminotransferase; AST = aspartate aminotransferase; BUN = blood urea nitrogen; CRP = C-reactive protein; GGT = gamma-glutamyl transferase; MCH = mean corpuscular hemoglobin; MCV = mean corpuscular volume; RBC = red blood cell; WBC = white blood cell

^a This result will be blinded baseline and up to the week 4 (day 29) visit.

10.3. Appendix 3: AEs and SAEs: Definitions and Procedures for Recording, Evaluating, Follow-up, and Reporting

10.3.1. Definition of AE

AE Definition

• An AE is any untoward medical occurrence in a clinical study participant, temporally associated with the use of IMP, whether or not considered related to the IMP• NOTE: An AE can therefore be any unfavorable and unintended sign (including an abnormal laboratory finding), symptom, or disease (new or exacerbated) temporally associated with the use of IMP

Events to be Collected as AEs

• Any abnormal laboratory test results (hematology, clinical chemistry, or urinalysis) or other safety assessments (eg, ECG, radiological scans, vital sign measurements), including those that worsen from baseline, considered clinically significant in the medical and scientific judgment of the investigator (ie, not related to progression of underlying disease)• Exacerbation of a chronic or intermittent pre-existing condition including either an increase in frequency and/or intensity of the condition• New condition detected or diagnosed after IMP administration even though it could have been present before the start of the study• Signs, symptoms, or the clinical sequelae of a suspected intervention-intervention interaction• Signs, symptoms, or the clinical sequelae of a suspected overdose of either IMP or a concomitant medication. Overdose per se will not be reported as an AE/SAE unless it is an intentional overdose taken with possible suicidal/self-harming intent. Such overdoses will be reported regardless of sequelae• Lack of efficacy or failure of expected pharmacological action per se will not be reported as an AE or SAE. Such instances will be captured in the efficacy assessments. However, the signs, symptoms, and/or clinical sequelae resulting from lack of efficacy will be reported as AE or SAE if they fulfill the definition of an AE or SAE

Events NOT to be Collected as AEs

• Any clinically significant abnormal laboratory findings or other abnormal safety assessments that are associated with the underlying disease, unless judged by the investigator to be more severe than expected for the participant's condition• The disease/disorder being studied or expected progression, signs, or symptoms of the disease/disorder being studied, unless more severe than expected for the participant's condition• Medical or surgical procedure (eg, endoscopy, appendectomy): the condition that leads to the procedure is the AE• Situations in which an untoward medical occurrence did not occur (social and/or convenience admission to a hospital)

- Anticipated day-to-day fluctuations of pre-existing disease(s) or condition(s) present or detected at the start of the study that do not worsen

10.3.2. Definition of SAE

An SAE is Defined as Any Untoward Medical Occurrence That, at Any Dose:
Results in death

Is life threatening
 
The term life threatening in the definition of serious refers to an event in which the participant was at risk of death at the time of the event. It does not refer to an event, which hypothetically might have caused death, if it were more severe.

Requires inpatient hospitalization or prolongation of existing hospitalization
 
 • In general, hospitalization signifies that the participant has been admitted at the hospital or emergency ward for observation and/or treatment that would not have been appropriate in the physician’s office or outpatient setting. Complications that occur during hospitalization are AEs. If a complication prolongs hospitalization or fulfills any other seriousness criteria, the event will be considered serious. When in doubt as to whether hospitalization occurred or was necessary, the AE is considered serious • Hospitalization for elective treatment of a pre-existing condition that did not worsen from screening will not be collected as an AE

Results in persistent or significant disability/incapacity
 
 • The term disability means a substantial disruption of a person’s ability to conduct normal life functions • This definition is not intended to include events of relatively minor medical significance such as uncomplicated headache, nausea, vomiting, diarrhea, influenza, and accidental trauma (eg, sprained ankle) that can interfere with or prevent everyday life functions but do not constitute a substantial disruption
Is a congenital anomaly/birth defect

Other situations:
 
 • Medical or scientific judgment will be exercised by the investigator in deciding whether SAE reporting is appropriate in other situations such as significant medical events that could jeopardize the participant or require medical or surgical intervention to prevent one of the other outcomes listed in the above definition. These events are usually considered serious • Examples of such events include invasive or malignant cancers, intensive treatment for allergic bronchospasm, blood dyscrasias, convulsions or development of intervention dependency or intervention abuse • Suspected transmission of any infectious agent via the IMP will also be considered an SAE

10.3.3. Recording and Follow-Up of AE and/or SAE

AE and SAE Recording

• When an AE/SAE occurs, it is the responsibility of the investigator to review all documentation (eg, hospital progress notes, laboratory reports, and diagnostics reports) related to the event• The investigator will then record all relevant AE/SAE information• It is not acceptable for the investigator to send photocopies of the participant’s medical records in lieu of completion of the required form• There can be instances when copies of medical records for certain cases are requested. In this case, all participant identifiers, with the exception of the participant number, will be redacted on the copies of the medical records before submission• The investigator will attempt to establish a diagnosis of the event based on signs, symptoms, and/or other clinical information. Whenever possible, the diagnosis (not the individual signs/symptoms) will be documented as the AE/SAE
Assessment of Severity

The investigator will assess intensity for each AE and SAE reported during the study. All AEs observed will be graded using the NCI CTCAE (version 5.0) definitions. The grade refers to the severity of the AE. If a particular AE’s severity is not specifically graded by the guidance document, the investigator is to use the general NCI CTCAE definitions of grade 1 through grade 5 following his or her best medical judgment, using the following general guideline:
 
• Grade 1: Mild; asymptomatic or mild symptoms; clinical or diagnostic observations only; intervention not indicated• Grade 2: Moderate; minimal, local or noninvasive intervention indicated; limiting age-appropriate instrumental ADL (eg, preparing meals, shopping for groceries or clothes, using the telephone)• Grade 3: Severe or medically significant but not immediately life-threatening; hospitalization or prolongation of hospitalization indicated; disabling; limiting self-care ADL (ie, bathing, dressing and undressing, feeding self, using the toilet, taking medications, and not bedridden)• Grade 4: Life-threatening consequences or urgent intervention indicated• Grade 5: Death related to AE 
NOTE: An AE that is assessed as severe may not necessarily meet the criteria for an SAE. Severe is a category used for rating the intensity of an event; and both AEs and SAEs can be assessed as severe. An event is defined as “serious” when it meets at least 1 of the predefined outcomes as described in the definition of an SAE, not when it is rated as severe. Grade 4 and 5 AEs are always assessed as serious (ie, SAE).

Assessment of Causality

• The investigator is obligated to assess the relationship between IMP and each occurrence of each AE/SAE as related or not related. The investigator will use clinical judgment to determine whether there is reasonable possibility that the IMP caused the AE

- A *reasonable possibility* of a relationship conveys that there are facts, evidence, and/or arguments to suggest a causal relationship, rather than a relationship cannot be ruled out
- Alternative causes, such as underlying disease(s), concomitant therapy, and other risk factors, as well as the temporal relationship of the event to IMP administration, will be considered and investigated
- **Related** means that the AE cannot be explained by the participant's medical condition, other therapies, or an accident. The temporal relationship between the AE and IMP administration is compelling and/or follows a known or suspected response pattern concerning that IMP
- **Not related** means that the AE can be readily explained by other factors such as the participant's underlying medical condition, concomitant therapy, or accident. No plausible temporal or biologic relationship exists between the IMP and the AE
- The investigator will also consult the investigator's brochure (IB) and/or product information, for marketed products, in his/her assessment
- For each AE/SAE, the investigator must document in the medical notes that they have reviewed the AE/SAE and has provided an assessment of causality
- There could be situations in which an SAE has occurred, and the investigator has minimal information to include in the initial report. However, it is very important that the investigator always assess causality for every event before the initial transmission of the SAE data
- The investigator could change his/her opinion of causality in light of follow-up information and send an SAE follow-up report with the updated causality assessment
- The causality assessment is one of the criteria used when determining regulatory reporting requirements

Follow-up of AEs and SAEs

- The investigator is obligated to perform or arrange for the conduct of supplemental measurements and/or evaluations as medically indicated or as requested to elucidate the nature and/or causality of the AE or SAE as fully as possible. This could include additional laboratory tests or investigations, histopathological examinations, or consultation with other health care professionals
- If a participant dies during participation in the study or during a recognized follow-up period, the investigator will provide a copy of any postmortem findings including histopathology
- The investigator will submit updated SAE data within 24 hours of receipt of the information

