8.4.6.1. Infections

Efgartigimod treatment leads to reduced IgG levels. As low IgG levels can be associated with increased infection risks, events in the MedDRA SOC Infections and Infestations are considered AESIs in this study. These events will be reported according to the timeframe specified in Section [8.4.1](#) and Section [10.3.4](#), with the following information provided:

- Causal pathogen
- Location of infection

- Relationship to an underlying medical condition, medical history, and concomitant medications
- Reoccurrence of a previous infection
- Any confirmatory procedure, culture, or urgent medical intervention

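### Protocol 10.3.3 asks for a causality call by reasonable possibility but defines 'Related' and 'Not related' by a different test, so an AE with two plausible causes can be classified either way

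*Protocol*

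**What the plan says.** The causality part of Protocol 10.3.3 does three things.

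- It requires a two-way call. The investigator must "assess the relationship between IMP and each occurrence of each AE/SAE as related or not related". There is no third category.
- It sets the standard: "The investigator will use clinical judgment to determine whether there is reasonable possibility that the IMP caused the AE". A reasonable possibility "conveys that there are facts, evidence, and/or arguments to suggest a causal relationship, rather than a relationship cannot be ruled out". Underlying disease, concomitant therapy and other risk factors are to be weighed; nothing here asks for them to be excluded.
- It defines the two answers. 'Related' "means that the AE cannot be explained by the participant's medical condition, other therapies, or an accident", followed by: "The temporal relationship between the AE and IMP administration is compelling and/or follows a known or suspected response pattern concerning that IMP". 'Not related' is an AE that other factors readily account for, followed by: "No plausible temporal or biologic relationship exists between the IMP and the AE".

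On infections, Protocol 8.4.6.1 makes the whole infections SOC an AESI and gives a biological reason: "As low IgG levels can be associated with increased infection risks". Protocol 6.9 (Table 4) permits stable conventional immunosuppressants, among them azathioprine, methotrexate and mycophenolate, and stable low-dose oral corticosteroids.

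Protocol 9.3.1 has all AEs summarised by relatedness. SAP 17.1.1 takes the investigator's two-way class as collected and uses it for the treatment-related and serious treatment-related TEAE summaries. Neither document has a rule for an AE with two plausible causes.

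**The concern.** The standard asks whether there is positive evidence for the IMP. The 'Related' definition asks whether everything else has been excluded. The 'Not related' definition asks whether the IMP has been excluded. These are three different questions, and the form takes only one of two answers.

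The conflict is sharpest for the study's only AESI. An infection under an IgG-lowering agent has a mechanism that the protocol itself states. If the participant also takes an immunosuppressant, it has a competing explanation too. Protocol 8.4.6.1 requires each infection report to describe how the event relates to underlying conditions and concomitant medication. Sites are therefore asked to record exactly the kind of information that, read literally, bars 'Related'.

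At stake are the treatment-related and serious treatment-related TEAE tables, including the event rate per 100 patient-years in the overview table. So is the causality input that Protocol 10.3.3 names as one criterion for regulatory reporting. The study has one open-label arm and no data monitoring committee, so investigator attribution has no concurrent control to set it against.

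**Working it through.** The plan gives no figure to reproduce: it states no expected infection rate or related-AE rate. The check is therefore one of logic, followed by a labelled illustration.

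**Step 1. Inputs.** The definitions in Protocol 10.3.3 turn on three attributes of an AE:

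- alternative explanation: none, possible but not ready, or ready;
- compelling timing or a known or suspected pattern: yes or no;
- any plausible temporal or biological link to the IMP: yes or no.

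That gives 3 × 2 × 2 = 12 combinations. A compelling pattern implies a plausible link, which removes 3 and leaves 9.

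**Step 2. Apply the definitions.** Each definition is two sentences with no connective, so three readings are possible.

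| Alternative | Pattern | Link | Both sentences needed | Either sentence enough | First sentence only |
|---|---|---|---|---|---|
| none | no | no | neither | both | Related |
| none | no | yes | neither | Related | Related |
| none | yes | yes | Related | Related | Related |
| possible | no | no | neither | Not related | neither |
| possible | no | yes | neither | neither | neither |
| possible | yes | yes | neither | Related | neither |
| ready | no | no | Not related | Not related | Not related |
| ready | no | yes | neither | Not related | Not related |
| ready | yes | yes | neither | both | Not related |

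Counts out of 9:

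- both sentences needed: 1 Related, 1 Not related, 7 neither;
- either sentence enough: 3 Related, 3 Not related, 2 both, 1 neither;
- first sentence only: 3 Related, 3 Not related, 3 neither.

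The cells are unweighted and say nothing about how often each kind of AE occurs.

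**Step 3. The dual-cause infection (last row).** It fits neither definition, or both, or only 'Not related', depending on the reading. Under the standard it can qualify as related, because the protocol's own IgG argument is an argument for causation and a competing cause does not cancel it. No reading of the definitions gives it 'Related' alone.

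**Step 4. Rules that might resolve it.** Protocol 9.3.1 counts a missing relationship as treatment-related, but that covers only blanks. SAP 17.1.1 takes the worst-case relationship over repeated events, which helps only if one occurrence was already called related.

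**Step 5. Illustration under assumed counts.** Take n = 30, the approximate upper number in Protocol 9.5. Assume that 6, 12 or 18 participants have an infection and that 25% to 75% of these are dual-cause. Participants affected: x = infected × share, rounded. The exact 90% interval runs from the 0.05 quantile of Beta(x, n − x + 1) to the 0.95 quantile of Beta(x + 1, n − x).

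- All called not related: they add 0/30 = 0% (0 to 9.5%).
- All called related, low case: 6 × 0.25 = 1.5, taken as 2; 2/30 = 6.7% (1.2 to 19.5%).
- Middle case: 12 × 0.50 = 6; 6/30 = 20.0% (9.1 to 35.7%).
- High case: 18 × 0.75 = 13.5, taken as 14; 14/30 = 46.7% (30.8 to 63.0%).

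These figures follow from the assumptions. They show only that, at this sample size, a few reclassified participants visibly change a related percentage.

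**The case against.** The strongest reply is that the direction is not settled. The 'Not related' wording blocks a dual-cause infection as firmly as the 'Related' wording does, since the protocol itself states a biological link. An investigator who follows the reasonable-possibility instruction can properly answer related, and the two rules in Step 4 lean the same way. This stands: a reader might infer that the definitions push infections towards 'not related' throughout the study, and the documents do not support that. What they support is inconsistency, with understatement where the exclusion wording is followed.

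The stake is also limited. A reader might take relatedness for a primary endpoint. It is not in the primary endpoint of Protocol Table 2 or in the SAP 17.1 list; it appears in supporting tables. AESIs count whether related or not, so no infection drops out of any AE, AESI or SAE total. SAEs and AESIs reach the sponsor within 24 hours whatever the causality call, and SUSAR reporting is the sponsor's task, so the regulatory effect is indirect. The study is descriptive, with no hypothesis test.

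Third, the finding that seven of nine cells have no home rests on requiring both sentences. That is right, and the gap shrinks under the other readings. The conflict with the standard survives all three, however.

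Finally, the dual-cause infection should not be called typical. Table 4 says what is permitted, not how many participants take it.

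**Conclusion.** The point holds as an internal contradiction. Protocol 10.3.3 states one causality standard and then defines the two permitted answers by another. An AE with a plausible IMP mechanism and another ready explanation can satisfy the standard and still have no single correct category. Two investigators can therefore classify the same event differently. Where the exclusion wording governs, treatment-related and serious treatment-related TEAEs are understated relative to the protocol's own standard.

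Total AE, AESI and SAE incidence is unaffected. The size of any understatement cannot be computed: the documents give neither the number of infections nor the share with competing causes, and the range in the illustration only reflects its assumptions. The conclusion does not depend on those counts, nor on whether the definitions are read as needing one sentence or both.

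**What to change.** Use one criterion in Protocol 10.3.3. 'Related' means there is a reasonable possibility, in the sense the section already gives, that the IMP caused the AE, even if another cause is also possible. 'Not related' means there is no such reasonable possibility. Keep alternative causes and timing as factors to consider, not as separate tests; the clauses "means that the AE cannot be explained by the participant's medical condition, other therapies, or an accident" and "No plausible temporal or biologic relationship exists between the IMP and the AE" should then no longer act as conditions. Use the same wording in the eCRF guidance and refer to it in SAP 17.1.1. The wording should stay with causation as the section has it and add no new test.

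The cost is a wording amendment and site communication. Somewhat more events may be classed as related. If AE collection has begun, the change puts two standards into one small dataset, so events assessed under the old wording should be re-reviewed or flagged in the listings. The parent study's definitions are not in these documents, so comparability with its related-event tables would need a separate check.
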